#### 5.3 Analysis of population characteristics

#### 5.3.1 Descriptive statistics

All background data such as patient characteristics, socio-economic characteristics, endometriosis pattern and gynecological history, family and medical history, concomitant medication as well as mood will be described by presenting frequency distributions and/or basic summary statistics (number of patients with an observation [n], mean, standard deviation [SD], median, 25th [Q1] and 75th [Q3] percentiles, minimum [Min] and maximum [Max]). Unless otherwise specified, the mean and median for a continuous variable will be listed to 1 more decimal place than the original (raw) values and the SD will be listed to 2 more decimal places than the original values. The minimum and maximum will be listed to the same number of decimal places as the original values.

Categorical variables will be summarized using frequencies and percentages. Each table will list both absolute and relative numbers (%), providing the total amount of available data for each variable. Total number of women (100%) for the presented (sub-) population is given in the first line of each table. Additional categories may be derived from data and are denoted by <<CATEGORY>> in the table templates. Percentages will be listed to 2 decimal places. In cases where the percentage calculated is > 0% and < 0.01%, three decimal places will be listed with the absolute value.

In addition, age-standardized proportions are presented for selected baseline characteristics, history of co-morbidity, risk markers and co-medication. Therefore, the most represented cohort will used as the referenced standard population.

#### 5.3.2 Stratifying factors

The numbers of patients enrolled and included in the analysis populations will be tabulated by defined stratifying variables for the AT and ITT population, if appropriate.

Baseline and follow-up population characteristics will be presented for the AT and ITT population and stratified by

Supporting document SOP BMT 01.09 – Doc 5002.02 – Effective date 21.03.2017

- (1) Country
- (2) EMT user type: starter vs. switcher vs. restarter
- (3) Diagnostic classification: Diagnosis confirmed by surgery vs. diagnosis based on clinical symptoms,

if not otherwise specified.

The analysis of the primary and secondary outcomes will be presented for the AT population, anemia and depression additionally for the ITT population. Primary and secondary outcomes are stratified by subgroups if appropriate:

- (1) Country
- (2) EMT user type: starter vs. switcher vs. restarter
- (3) Diagnostic classification: Diagnosis confirmed by surgery vs. diagnosis based on clinical symptoms

Selected outcomes regarding the baseline risk (lifetime history of co-morbidity, risk markers, co-medication, socio-demographic and lifestyle data), will be additionally displayed by subgroups as follows:

- (1) Age categories: < 20 vs. 20 to < 30 vs. 30 to < 40 vs. >= 40
- (2) Age standardized

Additional subgroups will be added for selected outcomes if appropriate.

#### 5.4 Analysis of primary and secondary outcome variables

The primary outcome (anemia, depression, treatment failure), secondary outcomes (risk factors, treatment pattern) as well as other safety outcomes (SAEs) and other outcomes of interest (surgeries) associated with the use of DNG, OAED and NAED will be assessed using different measurements as defined by Rothman et al. [8].

#### 5.4.1 Incidence measures

The *incidence rate* (IR) measures the occurrence of new cases per unit of person-time.

$$IR = \frac{Number\ of\ new\ cases}{Total\ follow - up\ time}$$

The incidence rate takes into consideration the patient-specific follow-up time and it assumes a constant hazard rate. For each of n subjects the time  $t_k (k=1,...,K)$  to: (1) the end of the risk period, if recurrent events are allowed or (2) to the first occurrence of a certain event is observed. If the event was not experienced, the (censored) time to the end of the risk period is observed.

In the present study, women-years are conducted as a unit of person-time. Incidence rates are shown per 10^4 women-years (WY) unless otherwise specified.

The *incidence rate ratio* (IRR) is the proportion of two incidence rate estimates.

$$IRR = \frac{Incidence\ rate\ of\ treatment\ group}{Incidence\ rate\ of\ control\ group}$$

Supporting document SOP BMT 01.09 – Doc 5002.02 – Effective date 21.03.2017

The incidence rate ratio gives a measure of how much more likely an event occurs in subjects under exposure (treatment group) than in subjects who were not exposed (control group).

The *incidence proportion* (IP) measures the occurrence of new cases in relation to the size of the population at risk within a given period of time (cumulative incidence).

$$IP = \frac{Number\ of\ new\ cases}{Size\ of\ population\ at\ risk}$$

Exact 95% confidence intervals for prevalence, incidence proportion, incidence rate, and incidence rate ratio will be calculated in accordance with Clopper and Pearson[9].

#### 5.4.2 Regression models

Regression analysis will be performed if a sufficient number of confirmed events are available for estimation, i.e. n≥5 confirmed events in each of the comparison groups.

Potential confounders such as

- age, personal and family history of depression, history of anemia, history of bleeding disorders and severity of pain will be included as time-invariant cofactors.
- EMT user type at follow up, use of Antidepressants/SSRI and current or worsening depression (primary outcome) will be included as time-dependent cofactors.

For each primary outcome, a summary table with predefined potential prognostic factors and the corresponding relative risk estimators is provided.

The final decision on the confounding variables will be made by the Safety Monitoring and Advisory Council:

Primary outcome variable	Predefined Prognostic Factors 	
Anemia	Age, history of anemia, history of bleeding disorders	
Depression	Age, family and personal history of depression, use of Antidepressants/SSRI	
Treatment Failure	Age, family and personal history of depression, severity of pain	

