APPENDIX 1: VALIDATION OF SELF-REPORTED EVENTS

Anemia

- Definite Event:
 - Confirmed by repeated reliable laboratory test (e.g. hemoglobin, packed cell volume), plus pertinent therapy (blood or iron transfusion, iron tablets) and
 - No obvious explanation (such as gastrointestinal bleeding, trauma, major surgery) or no explanation other than endometriosis related bleeding⁹
- Probable Event:
 - No reliable laboratory data available, but clinical diagnosis stated by a physician, followed by pertinent therapy (see above) and
 - No obvious explanation (such as gastrointestinal bleeding, trauma, major surgery) or no explanation other than endometriosis related bleeding⁹
- Event not confirmed:
 - Diagnosis reported by the patient is excluded by diagnostic procedures
 - A different medical condition is diagnosed by the attending physician
 - The woman did not contact a health professional to clarify her symptoms and no diagnostic measures were performed that could have clarified the diagnosis

Definite and probable events will be classified as 'confirmed events'.

Clinically relevant Depression

- Definite Event:
 - Diagnosis is confirmed by a physician specialized in psychiatry using validated instruments (e.g. HAM-D, BECK depression inventory)¹⁰
 - Confirmed suicide or attempted suicide in a participant with a past history of depression
- Probable Event:
 - Clinical diagnosis confirmed by physician specialized in psychiatry without the use of validated instruments (see above)¹⁰
 - Confirmed (attempted) suicide without a previous psychiatric diagnosis

⁹ Original wording: "Anemia is associated with prolonged, excessive or irregular bleeding". Revised on request of the Safety Monitoring and Advisory Council.

¹⁰ Bipolar disorders and schizoaffective disorders are excluded. This specification was added on request of the Safety Monitoring and Advisory Council.

- Event not confirmed:
 - Diagnosis reported by the patient is excluded by diagnostic procedures
 - Diagnosis is confirmed by a physician without specialized training in psychiatric diseases
 - A different medical condition is diagnosed by the attending physician
 - The woman did not contact a health professional to clarify her symptoms and no diagnostic measures were performed that could have clarified the diagnosis

Definite and probable events will be classified as 'confirmed events'.

Other Serious Adverse Events

• Definite Event:

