#### 5.4.2.1 Cox Proportional Hazard Model

Time-to-event (survival) analyses will be undertaken using Cox proportional hazard models (Cox model) to describe how the hazard increases for each unit increase of the regressor variables. Crude and adjusted hazard ratios (HR) comparing subpopulations under study will be calculated for all primary outcomes and 95% HR confidence limits (Wald) are provided. The crude model refers to a univariable model which includes exposure as the only explanatory factor. Potential predefined event-specific prognostic factors (section 5.4.2) are included in multiple models. In the Cox model, recurrent events are included.

18

 See Appendix III for all potential prognostic factors for each primary and secondary outcome.

Supporting document SOP BMT 01.09 – Doc 5002.02 – Effective date 21.03.2017

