## III List of potential prognostic factors for primary outcomes

Primary Outcome	Predefined Potential Prognostic Factors
Anemia	EMT user type at follow-up, age, history of anemia, history of bleeding disorders
Depression	EMT user type at follow-up, age, family and personal history of depression, use of Antidepressants/SSRI, severity of pain
Treatment Failure	EMT user type at follow-up, age, family and personal history of depression, current/worsening depression, severity of pain

Supporting document SOP BMT 01.09 – Doc 5002.02 – Effective date 21.03.2017

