### Section C-3.10 Incidence rate of self-reported depression

Table C-3.10.1 Incidence rate of self-reported depression, AT population, Compete cohort

	DNG		OAED			NAED		Allocation unknown	Total
		GnRH-a	Danazol	All OAED	СС	Other progestin	All NAED		
Number of women years	xx	xx	xx	xx	xx	xx	xx	xx	xx
Self-reported depression	xx	xx	xx	XX	xx	xx	XX	xx	XX
IR* (95% CI)	xx.x (xx.x-x.x)	xx.x (xx.x-x.x)	xx.x (xx.x-x.x)	xx.x (xx.x–x.x)					
Thereof									
Confirmed	xx	xx	xx	xx	xx	xx	xx	xx	XX
	xx.x (xx.x-x.x)	xx.x (xx.x-x.x)	xx.x (xx.x-x.x)	xx.x (xx.x-x.x)					
Not confirmed	xx	xx	xx	xx	xx	xx	xx	xx	XX
	xx.x (xx.x-x.x)	xx.x (xx.x-x.x)	xx.x (xx.x-x.x)	xx.x (xx.x-x.x					
Thereof									
Recurrent depression	xx	xx	xx	xx	xx	xx	xx	xx	XX
	xx.x (xx.x-x.x)	xx.x (xx.x-x.x)	xx.x (xx.x-x.x)	xx.x (xx.x-x.x)					
Potential depression,	xx	xx	xx	xx	xx	xx	xx	xx	XX
no further clarification	xx.x (xx.x-x.x)	xx.x (xx.x-x.x)	xx.x (xx.x-x.x)	xx.x (xx.x-x.x)					
possible									
Depression treated by	xx	xx	xx	XX	XX	xx	xx	XX	XX
GP	xx.x (xx.x-x.x)	xx.x (xx.x-x.x)	xx.x (xx.x-x.x)	xx.x (xx.x-x.x)					
Depressive disorders	XX	xx	xx	XX	XX	XX	XX	XX	XX
treated by psychologist	xx.x (xx.x-x.x)	xx.x (xx.x-x.x)	xx.x (xx.x-x.x)	xx.x (xx.x-x.x)					
Other psychiatric	XX	xx	xx	XX	XX	XX	XX	XX	XX
disorders**	xx.x (xx.x-x.x)	xx.x (xx.x-x.x)	xx.x (xx.x-x.x)	xx.x (xx.x-x.x)					
Other psychic	xx	xx	xx	XX	XX	xx	xx	xx	xx
problems***	xx.x (xx.x-x.x)	xx.x (xx.x-x.x)	xx.x (xx.x-x.x)	xx.x (xx.x-x.x)					
"No event" - before	xx	xx	XX	xx	xx	xx	xx	xx	xx
study, repetition	xx.x (xx.x-x.x)	xx.x (xx.x-x.x)	xx.x (xx.x-x.x)	xx.x (xx.x-x.x)					

Supporting document SOP BMT 01.09 – Doc 5002.02 – Effective date 21.03.2017

Note: \* Incidence rate is shown per 10^4 women years.

Note: \*\* Includes e.g. schizophrenia, bipolar, anxiety, eating disorders.

Note: \*\*\* Includes e.g. mood changes, psychosomatic disorders, no HCP visited.

Table C-3.10.2 Incidence rate of self-reported depression, AT population, Starter
Table C-3.10.3 Incidence rate of self-reported depression, AT population, Switcher
Table C-3.10.4 Incidence rate of self-reported depression, AT population, Restarter
Table C-3.10.5 Incidence rate of self-reported depression, AT population, Diagnosis confirmed by surgery
Table C-3.10.6 Incidence rate of self-reported depression, AT population, Diagnosis based on clinical symptoms
Table C-3.10.7 Incidence rate of self-reported depression, AT population, Germany

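### The depression Cox model adjusts for time-updated antidepressant use with no rule that the value precede the event, and country is in no SAP covariate list.

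*SAP*

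**What the plan says.** **Depression covariates.** SAP 5.4.2 lists the time-dependent terms: "EMT user type at follow up, use of Antidepressants/SSRI and current or worsening depression (primary outcome) will be included as time-dependent cofactors". Its table gives the depression model as "Age, family and personal history of depression, use of Antidepressants/SSRI". SAP Appendix III gives "EMT user type at follow-up, age, family and personal history of depression, use of Antidepressants/SSRI, severity of pain". Protocol section 11 had proposed age, chronic pelvic pain, anxiety disorder and family history, without antidepressant use.

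**Timing.** Neither document has a lag, a last-value-before-event rule or a start-date requirement for this covariate. The carry-forward rule in SAP 5.5 and Appendix IV concerns items such as the mood score. Forms are 6 to 12 months apart (SAP section 3). On the follow-up form (SAP Appendix II), question 3 asks for the month and year of a depression diagnosis. Question 4 asks for regular medication without dates.

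**What counts as an event.** Protocol Appendix 1 treats a case as not confirmed when "Diagnosis is confirmed by a physician without specialized training in psychiatric diseases". Mock Table C-3.10.1 puts the row "Depression treated by" GP under its not-confirmed heading, and also the row "Recurrent depression". SAP 5.4.2.1 says "In the Cox model, recurrent events are included".

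**Deciding estimate.** SAP 5.2 compares an upper confidence limit with the margin of 2. SAP 5.4.2.1 produces crude and adjusted hazard ratios. Neither section says which is compared.

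**Country.** Protocol section 11 names it as an example of a confounder the SMAC may add, and promises alternative analyses. It is in neither cofactor list of SAP 5.4.2, nor in the table there, Appendix III or the footnote to mock Table D-1.1.2 (anemia). SAP 5.3.2 and section 8 do stratify outcome tables by country.

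**The concern.** Adjusting for a variable that treatment or the outcome can change removes part of the effect being estimated. Here there are two routes.

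- **Reverse recording.** A woman is diagnosed during an interval, starts an antidepressant, and reports both on the next form. If that form's value is used for the interval, treatment of the event is entered as a predictor of the event.
- **Pathway.** A woman develops depression on treatment, a GP prescribes an antidepressant, and she becomes a confirmed case only later, when a psychiatrist is involved. Antidepressant use then lies between treatment and the counted event.

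Both routes pull the estimate toward 1. In a non-inferiority test of harm (H0: hazard ratio of at least 2), that makes a harmful drug easier to pass. Reporting the crude ratio as well does not solve this: it contains no covariates, so a gap between crude and adjusted does not isolate the antidepressant term.

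Country is a separate matter. Six countries contribute, and confirmation needs a psychiatrist, so confirmed rates could differ between countries. If drug mix also differs, the hazard ratio is confounded. Rate tables by country would show such a pattern but would not adjust the ratio.

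**Working it through.** **1. Reproduce the plan's figure (SAP Table 3).** Inputs: hazard ratio 2, one-sided alpha 0.0083, power 90%, 2:1 exposure, 0.01 events per woman-year.

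Events = (2.395 + 1.282)² / [(2/3)(1/3)(ln 2)²] = 13.52 / 0.1068 = 126.6, so 127. Then 127 / 0.01 = 12,700 women-years, or 8,467 DNG and 4,233 reference. With DNG at 10% the total is about 84,670. The plan states 8,400, 4,200 and 84,000, so it reproduces. The required women-years are not in question.

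**2. Convert attenuation to error.** At a true ratio of 2, DNG events = 8,400 × 0.02 = 168 and reference events = 4,200 × 0.01 = 42. SE = √(1/168 + 1/42) = 0.1725. If adjustment multiplies the ratio by r, the chance of falsely declaring non-inferiority on the adjusted ratio is Φ(−ln r / 0.1725 − 2.394).

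| r | False non-inferiority |
|---|---|
| 1.00 | 0.83% |
| 0.99 | 0.98% |
| 0.967 | 1.39% |
| 0.952 | 1.75% |
| 0.90 | 3.73% |
| 0.867 | 5.86% |

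**3. Reverse recording alone, by hand.** Treat one year as one interval with true rates 0.02 and 0.01. Assume 60% of cases and 5% of non-cases are recorded as users.

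- Users: DNG 100.8 events among 512.4 women; reference 25.2 among 233.1. Mantel-Haenszel terms are 100.8 × 233.1 / 745.5 = 31.52 and 25.2 × 512.4 / 745.5 = 17.32.
- Non-users: DNG 67.2 among 7,887.6; reference 16.8 among 3,966.9. Terms are 22.49 and 11.18.
- Adjusted ratio = (31.52 + 22.49) / (17.32 + 11.18) = 1.895, about 5% below 2.

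With 30-90% of cases and 5-10% of non-cases recorded as users, the ratio runs from 1.99 to 1.77 (0.4% to 11% attenuation). Lower use among non-cases makes it worse: 90% against 2% gives 1.58. With equal true rates it is 1.00 in every combination.

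**4. Both routes, simulated.** The design has 900,000 women per scenario, 2:1, monthly steps to 36 months, and forms at 6, 12, 24 and 36 months. Personal history is 20%, borrowing the depression prevalence in protocol section 12. Everything else is assumed: history at 3-fold rate, family history 20% at 1.5-fold, baseline use 3.8-7.6% at 2-fold, 50-80% of new cases treated at once, background starts 1-2% and stops 15-50% a year, reference rate 0.008-0.014 a year. Personal and family history are in every model. The table gives the hazard ratio with the antidepressant term divided by the ratio without it, for first events at a true ratio of 2.

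| Coding | Share of first events after a GP-treated stage | Ratio |
|---|---|---|
| Baseline value | any | 0.999-1.004 |
| Previous form | any | 0.991-1.002 |
| Same form | none | 0.952-0.993 |
| Same form | 20% | 0.896-0.977 |
| Same form | 37-38% | 0.867-0.959 |

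At a true ratio of 1 the values were 0.994-1.013. At 0.75, same-form coding gave 1.018-1.071, so a protective effect is also pulled toward 1.

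**5. Shorter exposure.** The protocol introduction says danazol and GnRH agonists need to be stopped after 6-12 months, and SAP 5.1 moves women who stop to an ex-use cohort. A similar simulation limited to 12 months, with one central set of assumed inputs and a GP-treated stage before 0-38% of events, gave same-form ratios of 0.967-0.974 for first events. The lower ends in step 4 therefore rest on longer comparator exposure than the protocol describes.

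**6. Country, illustration only.** At a true ratio of 1, suppose rates differ 1.5-fold between two country groups, with 60% of DNG time and 40% of reference time in the low-rate group. The unadjusted ratio is (0.6 + 0.4 × 1.5) / (0.4 + 0.6 × 1.5) = 0.92. The mirror allocation gives 1.08. The documents supply neither shares nor rates by country, so even the sign is open.

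**The case against.** **Silence is not a plan for same-form coding.** This is correct. Carrying each form's value forward is a common reading, and under it the effect on first events is at most 1%. But same-form coding also complies with the SAP as written, and a safety test should not depend on which one the programmer chooses.

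**Current antidepressant use is a legitimate risk marker.** This is true where women switch, and it is why a lagged version belongs in a sensitivity analysis.

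**The depression outcome is not adjusted for itself.** A reader might infer that it is, because SAP 5.4.2 names current or worsening depression as a time-dependent term. Appendix III assigns that term only to treatment failure: "EMT user type at follow-up, age, family and personal history of depression, current/worsening depression, severity of pain". There it overlaps with depressive mood as a listed side-effect reason (mock Table C-1.3.1), which is a minor point.

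**Country has not been ruled out.** A reader might infer a decision to leave it out. The documents do not support that: the SAP list is open, the SMAC has the final choice, and the protocol promises alternative analyses. Rates by country and drug mix by country are to be tabulated. What stands is that no list contains it and no planned table adjusts for it. The protocol expected the decision before the first interim analysis of follow-up data.

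**Recurrence may not be a contradiction.** The Cox statement can mean repeated confirmed events, and the mock-table row can mean reported recurrences that fail the definition. The two need one clarifying sentence. Larger attenuation can be simulated if recurrent events count, but such figures hold the event count at 168 + 42 and assume long comparator exposure, so they are not used here.

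**Conclusion.** The gap is certain from the text: a listed time-dependent covariate in a non-inferiority safety model has no timing rule, and the form and event definition allow it to follow treatment or the event. The direction is toward 1, so a true harm would be understated. There is no bias at a ratio of 1.

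The size is not determinable from the documents. With the previous form's value it is negligible. With the same form's value it is a few percent to roughly 10% under assumed inputs. If the adjusted ratio decides, 10% attenuation would raise false non-inferiority from 0.83% to about 3.7% at planned exposure. A reader might infer that the non-inferiority result is unreliable as planned; that would need same-form coding, extreme inputs and long comparator exposure together, and the documents establish none of these.

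For country, the omission from every SAP covariate list is established; a bias is not. This should be corrected before analysis, with medium confidence in its practical importance.

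**What to change.** 1. In the main depression model, use antidepressant/SSRI use at baseline (already in mock Table B-9.1.1) as a time-invariant covariate.
2. Add a sensitivity analysis with use lagged by one questionnaire.
3. Account for country in the Cox models, by stratification or as a covariate, pooling small countries where one arm has few women.
4. State that the adjusted hazard ratio is compared with the margin.
5. Reconcile SAP 5.4.2.1 with mock Table C-3.10.1 on whether recurrent depression is an event.
6. As a minor item, leave current or worsening depression out of the main treatment-failure model.

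**Cost.** SAP wording, model statements and one extra analysis; no new data. Baseline use becomes dated for women who switch later. In a simulated case (60% of OAED users leaving at month 12, antidepressant users half or twice as likely to move to DNG) the baseline-coded ratio was 1.956 to 1.967 against 1.961 without such channelling. Only that pattern was tested, and the lagged analysis covers the rest. Country strata without both arms at risk contribute no information. That matters because SAP 3.1 reports OAED recruitment well below target, and it is the reason for allowing pooling.

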Crude as well as adjusted hazard ratios will be calculated. The appropriate confounding variables will be built into the statistical model. Based on the expectation of a small absolute number of serious outcomes of interest the number of confounding variables will be limited to established risk factors for these outcomes. For anemia these will include age, duration of current use, and family history of bleeding disorders and a past history of anemia. For depression, age, chronic pelvic pain, anxiety disorder and a family history of depression are proposed. For 'treatment failure' chronic pelvic pain, age and previous surgical treatment will be included. The final decision on and the addition of other confounding variables (e.g. country) will be made by the Safety Monitoring and Advisory Council before the first interim analysis of follow-up data. In addition, alternative analysis will be performed with other potential baseline risks to check the appropriateness of this decision.

A detailed statistical analysis plan will be developed by the Principal Investigator during the first year after study start. The final analysis plan will be approved by the Safety Monitoring and Advisory Council before the first interim analysis of follow-up data.

Biannual interim reports will be provided to the funder following release of the interim analyses results by the independent Safety Monitoring and Advisory Council (cf. section 13).

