#### Treatment Failure

Treatment failure is defined as:

- 1. Medication ineffective given as a reason for stopping or switching treatment
- 2. Side effects of medication given as a reason for stopping or switching treatment

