#### Section C-1.3 Incidence proportions of treatment discontinuation due to treatment failure

Table C-1.3.1 Incidence proportions of treatment discontinuation due to treatment failure, AT population, Complete cohort

	DNG		OAED			NAED		Allocation unknown	Total
		GnRH-a	Danazol	All OAED	СНС	Other progestin	All NAED		
Number of treatment starts	xx	xx	xx	xx	xx	xx	xx	xx	xx
Treatment failure	xx	xx	xx	xx	xx	xx	xx	xx	xx
IP* (95% CI) Thereof**	xx.x (xx.x–x.x)	xx.x (xx.x–x.x)	xx.x (xx.x-x.x)	xx.x (xx.x-x.x)	xx.x (xx.x–x.x)	xx.x (xx.x-x.x)	xx.x (xx.x–x.x)	xx.x (xx.x–x.x)	xx.x (xx.x–x.x)
Medication ineffective	xx xx.x (xx.x–x.x)			xx xx.x (xx.x–x.x)	xx xx.x (xx.x-x.x)		xx xx.x (xx.x–x.x)		
Side effects  Thereof***	xx xx.x (xx.x-x.x)				xx xx.x (xx.x–x.x)			xx xx.x (xx.x-x.x)	
Depression / Depressive mood	xx xx.x (xx.x-x.x)			xx xx.x (xx.x–x.x)	xx xx.x (xx.x–x.x)			xx xx.x (xx.x–x.x)	
<category>></category>	xx xx.x (xx.x–x.x)			xx xx.x (xx.x-x.x)	xx xx.x (xx.x–x.x)			xx xx.x (xx.x–x.x)	

Note: \* Incidence proportion is shown per 10^2 treatment starts, including incident exposure at study entry, switches between exposure groups and/or restarts within exposure groups.

Note: \*\* Multiple answers possible.

Note: "Multiple answers possible. Only side effect categories with a proportion > 1% were displayed

Table C-1.3.2	Incidence proportions of treatment discontinuation due to treatment failure, AT population, Starter
Table C-1.3.3	Incidence proportions of treatment discontinuation due to treatment failure, AT population, Switcher
Table C-1.3.4	Incidence proportions of treatment discontinuation due to treatment failure, AT population, Restarter
Table C-1.3.5	Incidence proportions of treatment discontinuation due to treatment failure, AT population, Diagnosis confirmed by surgery
Table C-1.3.6	Incidence proportions of treatment discontinuation due to treatment failure, AT population, Diagnosis based on clinical symptoms
Table C-1.3.7	Incidence proportions of treatment discontinuation due to treatment failure, AT population, Germany
Table C-1.3.8	Incidence proportions of treatment discontinuation due to treatment failure, AT population, Poland
Table C-1.3.9	Incidence proportions of treatment discontinuation due to treatment failure, AT population, Hungary
Table C-1.3.10	Incidence proportions of treatment discontinuation due to treatment failure, AT population, Switzerland

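### The SAP contradicts itself on whether the treatment-failure model adjusts for depression arising on treatment; if it does, the adjusted HR is no longer a total effect and would favour DNG if DNG raises depression more than OAED

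*SAP*

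**What the plan says.** Four places bear on the covariates for treatment failure.

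- **SAP 5.4.2, bullet list.** "EMT user type at follow up, use of Antidepressants/SSRI and current or worsening depression (primary outcome) will be included as time-dependent cofactors". The bullet does not say which outcome model each factor enters.
- **SAP Appendix III, treatment-failure row.** "EMT user type at follow-up, age, family and personal history of depression, current/worsening depression, severity of pain". On-treatment depression appears for this outcome only.
- **SAP 5.4.2, table of predefined factors, treatment-failure row.** "Age, family and personal history of depression, severity of pain". On-treatment depression is absent. A footnote to this table refers to Appendix III for all potential factors.
- **Protocol section 11.** "For 'treatment failure' chronic pelvic pain, age and previous surgical treatment will be included". On-treatment depression is absent here too.

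SAP 5.4.2.1 adds: "Potential predefined event-specific prognostic factors (section 5.4.2) are included in multiple models". Section 5.4.2 also says: "The final decision on the confounding variables will be made by the Safety Monitoring and Advisory Council".

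On the outcome, SAP 5.4.3 counts as treatment failure "Side effects of medication given as a reason for stopping or switching treatment", and mock Table C-1.3.1 has a side-effect row "Depression / Depressive mood".

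**The concern.** A model for the effect of a drug on stopping treatment should not hold constant something the drug may cause and that then leads to stopping. On-treatment depression fits that description. It arises after treatment starts, it can be the reason for stopping, and stopping for that reason is counted as failure. A hazard ratio that conditions on it compares women within the same depression status and leaves out the part of the drug's effect that runs through depression.

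Timing adds to the difficulty. The follow-up questionnaire (SAP Appendix II) collects both the depression diagnosis and the end of treatment by month and year, so the order of the two will often be uncertain.

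The direction matters because treatment failure is the outcome on which DNG is tested for superiority, and a possible effect of DNG on mood is one of the reasons given for the study. If DNG raises depression more than OAED does, the adjusted ratio is too favourable to DNG.

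**Working it through.** **The plan's own figure.** SAP Table 4 uses failure 0.30 in the reference cohort and 0.25 in DNG, one-sided alpha 0.0167, power 90%, and 2:1 allocation. It arrives at 1,475 and 2,950 women-years. A two-proportion calculation with unpooled variance and continuity correction gives 1,442 and 2,884, which is 2.2% lower. Power at the stated numbers is 0.918. The table therefore reproduces, and this point disputes none of its figures. The rest is an illustration of bias.

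**Inputs from the documents.** Failure 0.30 and 0.25, used here as yearly hazards among women without depression, so the direct ratio is 0.25/0.30 = 0.833. Depression at least 0.01 per woman-year (SAP section 4). Depression HR of 2, the non-inferiority limit (SAP 5.2).

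**Assumptions not in the documents.** Constant hazards; 3 years of follow-up; depression multiplies the failure hazard by m = 3, 10 or 30 in both cohorts; and, as a second scenario, 0.05 depressions per woman-year in the reference.

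**A simple bound.** If DNG doubled depression from 0.01 to 0.02, there would be 0.01 extra depressions per woman-year. Even if each ended in failure, that is 0.01/0.25 = 4% of the DNG failure rate, and 0.01/0.05 = one fifth of the planned difference.

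**Model.** Let λ be the failure hazard without depression, μ the depression rate and T = 3. Expected time per woman:

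- without depression: A = (1 − e^(−(λ+μ)T)) / (λ+μ)
- with depression, still on treatment: B = μ/(λ+μ−mλ) × [(1 − e^(−mλT))/(mλ) − A]

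Overall failure rate = (λA + mλB)/(A + B). The ratio of these rates between cohorts is the result without the depression term. The result with the term is 0.833 by construction.

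**One case in full** (m = 10, depression 0.01 in the reference, HR 2):

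- Reference: λ = 0.30, μ = 0.01, A = 1.953, B = 0.0060, rate 0.308.
- DNG: λ = 0.25, μ = 0.02, A = 2.056, B = 0.0149, rate 0.266.
- Ratio 0.863 without the term, 0.833 with it: a shift of −3.5%.

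| Depression in reference (per WY) | Depression HR, DNG vs reference | Failure HR without the term, m = 3 / 10 / 30 | With the term | Shift from adjusting |
|---|---|---|---|---|
| 0.01 | 1 | 0.835 / 0.837 / 0.838 | 0.833 | −0.1% to −0.6% |
| 0.01 | 2 | 0.849 / 0.863 / 0.868 | 0.833 | −1.8% to −4.0% |
| 0.05 | 1 | 0.839 / 0.850 / 0.855 | 0.833 | −0.7% to −2.5% |
| 0.05 | 2 | 0.901 / 0.965 / 0.988 | 0.833 | −7.5% to −15.7% |

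A simulation with 3,000,000 women per cohort and Poisson regression at m = 10 agreed. Without and with the term it gave 0.837 and 0.833 (0.01, HR 1), 0.866 and 0.836 (0.01, HR 2), and 0.966 and 0.833 (0.05, HR 2).

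**The case against.** The strongest reply is that the intended model may not contain the variable at all. SAP 5.4.2.1 takes event-specific factors from section 5.4.2, and the only list there arranged by outcome is the table, which omits it. Appendix III is headed as a list of potential factors and can be read as a wider pool. The bullet can be read as describing how factors are coded rather than which model they enter. The footnote to the anemia shell (Table D-1.1.2) supports this: its adjustment set matches the short table and leaves out user type at follow-up, which the bullet and Appendix III both name. The advisory council also has the last word. All of this stands, so a reader who infers that the treatment-failure model definitely adjusts for on-treatment depression goes further than the documents do. It does not remove the contradiction, because the bullet says the factor will be included and the treatment-failure shell in Section D-3 carries no footnote to settle it.

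Second, a reader might infer that all DNG failures due to mood would be adjusted away. They would not. The covariate is the primary outcome, that is, depression confirmed by a psychiatric specialist, or confirmed suicide or attempted suicide. Depression treated only by a general practitioner counts as not confirmed, and the stopping reason in Table C-1.3.1 is self-reported. The crude HR, the incidence rate ratio and failures by reason are all reported without this adjustment.

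Third, the bias favours DNG through this route only if DNG raises depression more than OAED, while SAP 5.2 assumes that no approved treatment raises it. Protocol section 1 also notes that depression may be a sequela of the disease, so on-treatment depression could be a time-varying confounder as well as a mediator. That is a reason to examine it separately. An ordinary time-dependent covariate does not separate the two roles.

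**Conclusion.** The contradiction between the 5.4.2 bullet and Appendix III on one side, and the 5.4.2 table and protocol section 11 on the other, is plain on the face of the documents. If the former are followed, the adjusted treatment-failure HR does not estimate the total effect of DNG, and it is biased towards DNG when DNG raises depression more than OAED.

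At the plan's depression rate the size is modest: 2-4% on the hazard ratio if DNG sits at the depression margin of 2, and under 1% if depression risk is equal. At an assumed 0.05 per woman-year with HR 2, adjusting lowers the ratio by about 7-16%; with equal risk at that rate it lowers it by 0.7-2.5%. These figures rest on the assumed 3- to 30-fold multiplier, constant hazards and the 3-year horizon. The planning rate is stated as a minimum, so the larger scenario cannot be excluded in advance.

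It would be tempting to say that the adjustment could turn no advantage into a 17% reduction in failure. That needs depression at 0.10 per year on DNG against 0.02 on OAED, a ratio of 5, together with stopping at 3 per year once depressed. The documents support none of these inputs. Nor do they show that the superiority test would be decided by this term: SAP 5.2 states the hypothesis as an odds ratio, Section D-3 plans a rate ratio and crude and adjusted hazard ratios, and no passage says which one decides.

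**What to change.** Delete current/worsening depression from the treatment-failure row of Appendix III, and from the time-dependent list in 5.4.2 for that outcome. The adjusted HR in Section D-3 then uses only the pre-treatment factors already in the 5.4.2 table: age, family and personal history of depression, and severity of pain. Add a footnote to the D-3 shell naming them, as the anemia shell does.

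If the role of mood in stopping is of interest, show a model with on-treatment depression as a labelled sensitivity or mediation analysis. It would also help to state which estimate decides superiority.

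The cost is SAP wording and one covariate fewer, with the advisory council's agreement on the list. No new data are needed.
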